1.0 SCHEMA

Figure 1. Study Design

2.0 OBJECTIVES

2.1 Primary Objectives

Aim 1: Using our enhanced telehealth techniques, determine if **patient activation**, self-efficacy, ostomy-related knowledge, and HRQOL will be improved and sustained over time in the online interactive communication Ostomy Self-Management Telehealth program (OSMT) curriculum compared to a usual care (UC) group.

Hypothesis 1.1: Taking into account time since surgery:

- 1.1.1 Survivors in the OSMT group will have greater improvement in **patient activation** compared to UC.
- 1.1.2 Survivors in the OSMT group will have a sustained improvement in **patient activation**.
- 1.1.3 In survivors in the OSMT group, higher attendance levels will be associated with increased **patient activation**.

Hypothesis 1.2: Taking into account time since surgery:

- 1.2.1 Survivors in the OSMT group will have greater improvement in **self-efficacy, ostomy-related knowledge, and HRQOL** compared to UC.
- 1.2.2 Survivors in the OSMT group will have a sustained improvement in **self-efficacy, ostomy-related knowledge, and HRQOL**.
- 1.2.3 In survivors in the OSMT group, higher attendance levels will be associated with increased **self-efficacy, ostomy-related knowledge, and HRQOL**.

2.2 Secondary Objective(s)

Aim 2: Determine the differences in ostomy-related **medical care utilization** and family **financial burden** imposed on survivors between OSMT and UC groups.

Hypothesis 2.1: OSMT telehealth subjects will use fewer **ostomy-specific family resources** in the 6 months after OSMT compared to UC subjects.

Hypothesis 2.2: OSMT telehealth subjects will use fewer **ostomy-specific health care services** in the 6 months after OSMT compared to UC subjects.

Question 2.1: What is the difference in the overall levels of **ostomy-related family financial burden** between OSMT and UC groups?

Question 2.2: What are types and levels of effort of OSMT intervention personnel and specific equipment, supplies, and informatics support required to implement and operate a successful OSMT program; what are participants' levels of use of ostomy-specific health care services and supplies; and what are the time and in-home requirements for participating in OSMT for survivors and their family caregivers. This information is required for replicating our OSMT intervention in the event that we find it improves the primary and secondary outcomes of OSMT participants.

3.0 BACKGROUND

An ostomy is the externalization of a tubular structure in the body. In the context of this proposal, it relates to intestines externalized to the abdominal wall. It adversely affects health-related quality of life (HRQOL) in a diverse population of cancer survivors. For cancer, ostomies are most commonly placed for rectal cancers, followed by urinary bladder cancer. Ostomies may be needed for other cancers related to bulky or metastatic disease, or in emergencies. In addition, ostomies may be placed on a temporary or a permanent basis. Temporary ostomies may be created in emergencies, such as perforation or obstruction due to tumor, or in planned

procedures, as with a low rectal resection for cancer where an ostomy is placed to “protect” a new anastomosis while it heals. Temporary ostomies may become permanent as a result of underlying comorbidities, need for other treatments related to cancer, or poor outcome of anastomosis (leak or stricture). Peri-operative needs are the same regardless of ostomy permanence; survivors should receive clear, systematic, evidence-based ostomy self-management instruction and support.

Cancer survivors with ostomies should have a confirmed level of self-management skills, as well as a commitment to self-management. Cognitive restructuring, problem solving, and self-efficacy/locus of control are essential tools for effective self-management. As in most chronic conditions, this tends to be long-term, complex, and multidimensional. Hit-or-miss ostomy care, nurse counseling, and community referral have been the primary modes of self-management education and support in the peri-operative period. **Clearly, ostomates face many obstacles in coping with their condition, not least of which is medical care that often does not meet their needs for effective information, clinical management, psychological support, and patient activation.**¹⁻⁶ Ostomates and their families must engage in ostomy self-management, make behavior changes, and adjust to the consequences of their condition, becoming the principal caretakers and navigators. Preparation of the survivor and unpaid designated caregivers (CGs) (usually family members) is important to assure optimal functioning and HRQOL, as well as to prevent or ameliorate ostomy-related complications and associated health care utilization.⁷ Multiple communication issues make it difficult for ostomy survivors to access resources for improving their self-management, and undermine opportunities to improve and sustain HRQOL. These resources include lack of consistent follow-up, travel issues, lack of surgeon focus on ostomy-related problems, and lack of ostomy nurse clinic resources.

Ostomies are associated with multiple HRQOL difficulties.⁸⁻¹² Ongoing problems include pouching care, travel out of the home, social interactions, intimacy, and acceptance of/satisfaction with appearance. Studies document persistent challenges including sexuality,^{11,13-26} psychological problems,^{7,8,10,11,15,26} and interference with work,^{17,28,29} and recreation and sporting activities.^{17,30-33} However, improved self-efficacy eases psychological and social burden of ostomies.³⁴ **No reports have been published on the results of a systematic ostomy self-management program to ensure optimal post-operative care, including adaptation, self-management, and ostomy comfort.**

Usual Care. Usual care (UC) in peri-operative and long-term settings is not standardized for ostomy patients. Usual care does not provide any formal, reproducible training for patients or CGs. It typically consists of an Ostomy Care Nurse (OCN) who works with patients and CGs concerning technical issues (fitting, emptying, supplies, surrounding skin care, etc.) while the new ostomate is still an inpatient. Therefore, prior to discharge, most survivors have begun learning to care for their ostomy but will continue learning (primarily on their own) after discharge. For some survivors, training may result in 1 - 2 extra hospital days, although patients are often required to leave hospitals earlier than in the past, leaving less time to adequately train. Additionally, early education is challenging since the bowel or bladder adaptations to surgical changes occur over a matter of weeks and months. Survivors are not typically given specific appointments to a wound care/ostomy clinic. Survivors with ostomies may receive ostomy care or advice in the context of other scheduled clinic appointments, and then only on an “as-needed” basis. Often, there are no recurring support groups or formal peer support systems for survivors with ostomies, and little or no matching of specific products to individual patient needs.

Support Groups. Some communities or health care systems provide contact information of a local ostomy support group chapter, but in our research group’s R01 study of Kaiser Permanente (KP) cancer survivors, only 22% of the ostomates reported attending available

ostomy support groups. In addition, even where a group is attended, the content is neither systematic, nor based on self-efficacy and skills enhancement, as in our proposed intervention. High levels of consumer satisfaction and outcome evaluations have documented the value of cancer support groups.³⁵ Research conducted on face-to-face support groups has revealed positive outcomes.³⁵ However, this research also reveals variations in rates of participation and attendance. Slevin and colleagues provided evidence that physician and nurse-led support groups were preferred by patients, but at least 20% of those invited did not join the group, and another 20% dropped out before the last session.³⁶ These numbers were approximately the same for Goodwin et al.—66% participated, and 19% dropped³⁷—and by Classen et al.—20% declined to participate and 20% dropped.³⁸ In contrast to the live groups, on-line groups conducted by CancerCare in New York City have had tremendous success recruiting people to virtual telephone groups and having them persist when multiple sessions were conducted.³⁹ Each of the four 1-hour long sessions on “Living With, Through and Beyond Cancer” had more than 3,000 callers. Clearly, participation through tele-communication can be more successful for cancer survivors than attending face-to-face support groups.

4.0 SIGNIFICANCE

Over one million individuals in the U.S. have ostomies.⁴⁰ The American Cancer Society estimates 39,610 rectal cancer cases and 74,000 bladder cancer cases will be diagnosed in 2015.⁴¹ Of these, at least 30,000 will receive ostomies, and an additional unknown number due to gynecologic, other gastrointestinal tumors. The HRQOL impact is tremendous and greater than with many other cancer treatments. An ostomy is often a prolonged or lifelong disabling problem for cancer survivors. The adaptation period is quite variable. In our R01 KP study, 18% of participants took at least one year, or never felt comfortable, in their ostomy care. Importantly, many patients cannot attend self-management programs or patient groups for a myriad of reasons, including distance to travel, monetary outlays, comorbidities making travel difficult, or lack of access to transportation. In addition, a national shortage of OCNs means patients with an ostomy, whether newly placed or a long-term issue, receive little help. It is imperative to study interventions for these cancer survivors aimed to limit family financial burdens, decrease medical care use, and improve well-being.

4.1 Inclusion of Women and Minorities

This study was designed to include women and minorities, but was not designed to measure differences of intervention effects. The anticipated accrual in the ethnicity/race and sex categories is shown in the table below.

Estimated Final Racial/Ethnic and Gender Enrollment Table

Race	Male (N)	Female (N)	Total (N)
American Indian/Alaska Native	0	0	0
Asian	4	6	10
Black/African-American	19	21	40
Hawaiian/Pacific Islander	0	0	0
White	45	47	92
Multi-race	1	3	4
Ethnicity	Male (N)	Female (N)	Total (N)
Hispanic (Latino/Latina)	8	10	18

Non-Hispanic	63	69	132
--------------	----	----	-----

5.0 ELIGIBILITY CRITERIA

5.1 Eligibility criteria

1. Cancer survivors over 21 years of age having undergone a procedure that needed an intestinal stoma (fecal or urinary). Survivors with temporary ostomies will be included.
2. All participants must have a full understanding of the protocol and be able to sign an informed consent form.
3. Having an identified caregiver is **not** a requirement for eligibility.
4. All participants will attend their first training session at least six weeks after their operation.
5. There is no maximum time since surgery.

6.0 STRATIFICATION FACTORS

Potential stratification factors are gender, medical center site, and fecal vs. urinary ostomy. Gender and site will be stratified in the randomization process, whereas ostomy type will be explored in the analysis.

7.0 REGISTRATION GUIDELINES

7.1 Registration Timing

Patients must be registered by the start time of the first intervention session.

7.2 Investigator/Site Registration

7.2.1 Study Accrual process

7.2.1.1 Patient Identification Patient identification will be variable by site as outlined below. For patients who are asked to participate, a log will be kept without any identifiable information. This log will simply record whether patient accepted or declined. If declined, the reason for declining will get recorded.

7.2.1.2 University of Pennsylvania

UP Research Coordinator will use lists of patients from EPIC records in the Colorectal (under the direction of [name]), Urology (under the direction of [name]), and Ostomy clinics (under the direction of WOCNs [name] and [name]) that have undergone an ostomy procedure. In addition, patients who are seen in these clinics will be asked if they are willing to be contacted regarding this study. These lists include patient names, uncoupled from clinical data.

7.2.1.3 City of Hope

Study CRA will work with site-PI ([name]) to identify appropriate candidates for the study. The CRA will work closely with the Departments of Medical Oncology and Department of Surgery to identify eligible participants. She will attend key meetings (ambulatory clinics, tumor boards) on a weekly basis and work with attending MDs to identify eligible participants. The attending MD will introduce the study to patients and obtain their permission for the CRA to contact them. With permission, the CRA will contact eligible participants and explain the study purpose, answer

questions, and ascertain interest in participation. Study objectives and procedures, and their attendant risks and discomforts, will be carefully explained to the participants.

7.2.1.4 Yale-New Haven

The Yale Research Assistant will work in collaboration with the site-PI ([name]) and site-Col ([name]) to identify potential participants for the study. Potential participants must meet eligibility criteria outlined in the study protocol. Potential areas of recruitment include the outpatient setting (ostomy or post-surgical clinics) and inpatient surgical units of the Yale New-Haven Hospital system and Smilow Cancer Center. The appropriate medical and nursing staff involved in the care of these patients will be contacted about the study a priori and a method of communication and referral will be established between the clinical and research staff. We will be in close touch with these referral sources on a daily basis to identify potential patients.

The clinical staff will approach the patient and ask for his or her permission for the RA to contact them. Having this permission, the RA will approach the patient to describe and explain the study purpose, study groups (OSMT training group versus Usual Care Group), randomization procedures, study procedures, and human subjects' protection concerns (right to withdraw, confidentiality, risks and benefits, etc.).

7.2.2 Randomization

Patients who meet eligibility criteria will be approached to enroll in the randomized telehealth intervention versus a usual care comparison group using an approved consent process (see Schema). **Consents will need to be signed and received prior to randomization.**

Subjects will be randomized using stratified permuted block randomization. Once consented, the participant will be randomized to OSMT or UC, using computer-generated random lists blocked by site and gender, and with assigned arm in sealed envelopes blind to investigators and coordinators until assignment. This means that each participating site will have a unique pair of computer-generated randomization lists, one for male and the other for female, ensuring balance by sex between intervention and usual care groups at each site without the need for communication with a data coordinating center core for each randomization. The randomization lists will be comprised of blocks of 4 with permuted patterns so that balance is achieved after multiples of 4 in each sex have been randomized.

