8.1 Session Information/Preparation

Site coordinators at the three accrual sites will communicate to each other the number of subjects being assigned to a group as they are randomized to the Intervention arm. When the group enrollment gets to six, they will close enrollment to that group and begin enrolling in the next group. Coordinators will slow enrollment if needed so that subjects are not enrolled in a group starting more than 2 months from the enrollment date. If needed, the team will discuss adding additional groups to the schedule on different dates so that subjects will be able to start within the 2-month window from enrollment date.

For intervention session schedules, the protocol will include two different schedules for intervention session administration. This design is to provide flexibility for participants and also to maximize study accrual and participation. The schedules include:

Schedule #1: Two sessions administered on the same day, with a break in between. There will be a 4-week interval between the first set of 2 sessions and second set of 2 sessions. The caregiver session will be held two weeks after the first set of sessions.

Schedule #2: One session administered per day, once a week over a five-week period. There will be a one-week interval between session 2 and session 3 during which the caregiver session will be held.

The two schedules vary throughout the study period based on participants' convenience and preference.

If a subject misses a session, they can make up just the missed session with the next 1 or 2 scheduled groups rather than start over with a new group. If they miss both Session 1 and Session 2, they can be re-assigned to the next group as long as the next group size doesn't

exceed 6, or at the ostomy nurses' ([name] and [name]) discretion if the group size would exceed 6.

If a subject misses Session 3 or Session 4 or both, they can make up the missed session(s) with the next 1 or 2 scheduled groups. If they miss both chances to make up the sessions, they will be asked to do the surveys and will be analyzed as a separate group using an intent-to-treat contrast.

To account for making up sessions or delays in completing interim surveys, for both intervention and usual care groups, the 6-month followup surveys will be requested from subjects 6 months after the date the interim surveys are completed.

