12.13 Sample Size and Power. Total potential sample size 240 (up to 120 per arm), to ensure at least 75 per arm completing the study with complete baseline COH-QOL-CRC scaled items, assuming a 15% dropout rate. This will maintain sufficient power for the COH-QOL-CRC scaled items. The larger sample size for the primary endpoints Patient Activation Measure (PAM) and ostomy management self-efficacy (SE) will provide 80% power to detect a 2.75 change in PAM and a 0.50 change in SE, which is not considered excessively powered. Detectable differences based on variances observed from our R21 for PAM and SE, as well as from our R01 for COH-QOL-CRC subscales. We changed two items slightly on the self-efficacy questions to make them ostomy-relevant. Our observed variation for ostomy management SE is consistent with the original form of symptom management SE across different patient samples reported by Lorig's group (SD range 2.1 to 2.4).⁵¹⁻⁵⁷ We will examine the reliability of these items and expect them to have a Cronbach's alpha of ≥ 0.75 . Calculated detectable differences were based on the following assumptions 1) alpha of 0.05, 2) within-subject correlation on repeated measures of 0.60. Estimates are based on repeated measures multivariable modeling, adjusted for baseline,

with two follow-up measurements. Also shown for comparison are two rough indices of clinically important differences. Sufficient research has not been performed on these scales to determine with certainty a minimal clinically-important difference that is anchored on participant self-assessment of health status. An alternative suggested by Sloan⁵⁸ is the empirical rule effect size (ERES) method to judge minimally important differences (MID) in outcome measures. We also present 50% of the observed sample SD, a common rule-of-thumb for clinically meaningful differences.⁵⁹ The table shows that even with substantial shortfall in sample size (down to 65 per group) we still can detect differences below the estimated MID.

Detectable Outcome Differences with 80% Power						
Measure	SD	N= 75	N=70	N=65	ERES⁵⁸	.5 SD⁵⁹
Patient Activation Measure	13	3.4	3.5	3.6	8.0	6.5
Ostomy self-management self-efficacy	2.3	0.60	0.62	0.64	0.80	1.2
COH-QOL-CRC Total	1.6	0.42	0.43	0.45	0.88	0.8
COH-QOL-CRC Physical	1.8	0.47	0.49	0.51	0.88	0.9
COH-QOL-CRC Psychological	1.8	0.47	0.49	0.51	0.88	0.9
COH-QOL-CRC Social	2.1	0.55	0.57	0.59	0.88	1.1
COH-QOL-CRC Spiritual	2.2	0.57	0.59	0.62	0.88	1.1

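### A fixed, published block size of 4 in each site-by-sex list makes up to one third of assignments deducible, so concealment is weaker than Protocol 12.11 claims

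*Protocol*

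**What the plan says.** Protocol 7.2.2 sets stratified permuted-block randomization in which "each participating site will have a unique pair of computer-generated randomization lists, one for male and the other for female". The block size is single and printed: "The randomization lists will be comprised of blocks of 4 with permuted patterns so that balance is achieved after multiples of 4". Assignments are held "with assigned arm in sealed envelopes blind to investigators and coordinators until assignment", and the scheme runs "without the need for communication with a data coordinating center core for each randomization". The same section requires signed consent to be in hand before a participant is randomized.

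Protocol 8.1 has site coordinators "communicate to each other the number of subjects being assigned to a group as they are randomized to the Intervention arm", and adds: "Coordinators will slow enrollment if needed so that subjects are not enrolled in a group starting more than 2 months from the enrollment date".

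Protocol 12.11 relies on blinding the assessment team up to the moment of assignment as the means of avoiding selection bias. Protocol 12.13 gives the size: "Total potential sample size 240 (up to 120 per arm".

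Neither document mentions varied or undisclosed block sizes. The SAP text does not discuss randomization.

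**The concern.** A sealed envelope hides the next card. It does not hide what the earlier cards in the same block imply. When the block size is constant and known, and past assignments are visible, the end of every block can be read off a simple tally. Past assignments are visible here: one arm attends scheduled video sessions and the other does not, and 8.1 shows that coordinators know of intervention assignments as they occur.

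At stake is selective enrollment. Someone who foresees the next arm can, without meaning to, influence whom to approach or when a consented patient is randomized. The primary outcome, the PAM, is self-reported. Characteristics such as motivation or ease with technology could affect both a recruiter's view of who suits a telehealth group and the patient's activation score. They are not among the candidate covariates listed in Protocol 12.2 and the SAP.

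**Working it through.** The documents state no predictability figure, so there is none to reproduce.

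**Inputs.**
- Block size 4, fixed (7.2.2).
- Allocation 1:1, so each block holds two of each arm (7.2.2 and 12.13).
- Lists: 3 sites × 2 sexes = 6 (7.2.2).
- Planned size up to 240 (12.13), so 240/6 = 40 per list on average.
- Assumption: the observer knows the block size and keeps a complete tally for one list.

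**Assignments known with certainty.** There are C(4,2) = 6 equally likely sequences. An assignment is certain once both places of one arm in the block are used.
- 1st and 2nd places: never certain.
- 3rd place: certain when the first two match, 2 of 6 sequences = 1/3.
- 4th place: always certain.

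Expected number per block = 0 + 0 + 1/3 + 1 = 1.333. Share = 1.333/4 = 33.3%. For 240 participants, 240/3 = 80 assignments; for 150 (75 per arm), 50. An incomplete last block lowers the share slightly: a list of 25 has six full blocks, giving 6 × 1.333 = 8 certain assignments, and 8/25 = 32%.

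**Best-guess accuracy.** The observer always guesses the arm with more places left.
- 1st place: 1/2.
- 2nd place: 2/3.
- 3rd place: (1/3)(1) + (2/3)(1/2) = 2/3.
- 4th place: 1.

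Mean = (0.500 + 0.667 + 0.667 + 1)/4 = 2.833/4 = 70.8%, against 50% under simple randomization.

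**Randomly varied block sizes.** These were simulated with 3,000 lists of 40 and an observer who knows the set of sizes, but not the size of any given block, and updates by Bayes' rule. Giving the observer the set is the cautious choice.

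| Block sizes | Known with certainty | Best-guess accuracy | Largest imbalance in a list |
|---|---|---|---|
| 4 (plan) | 33% | 71% | 2 |
| 4/6 | about 6% | about 69% | 3 |
| 2/4/6 | about 4% | about 70% | 3 |
| 4/6/8 | about 2% | about 68% | 4 |

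The largest imbalance is half the largest block. Varying the sizes removes most of the certain knowledge but hardly changes the guessing advantage.

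**The case against.** The strongest reply has four parts.

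First, the mechanism is only partly documented. A reader might infer that the same coordinators recruit, open the envelopes and track how the groups fill. The documents do not say so. They do not state who opens or holds the envelopes, and first contact is partly separated from the research staff: at City of Hope the attending physician introduces the study (7.2.1.3), and at Yale clinical staff make the approach (7.2.1.4). Nor does the count exchanged under 8.1 reveal a position in a block, because it is a one-arm total for a session group, pooled over sites and sexes. It shows that assignments are known, not that anyone keeps a tally by list. This stands.

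Second, there are safeguards. Consent must be received before randomization and may come back by mail (7.2.3), which weakens control over who takes the next envelope. Acceptances and refusals are logged (7.2.1.1), and data on eligible non-participants are collected where permitted (12.11). These limit selective enrollment or help to detect it. They leave one third of assignments deducible, and staff still influence whom to approach and when.

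Third, a reader might conclude that any resulting bias could not be adjusted away. That is too strong. The power calculation in 12.13 assumes adjustment for baseline, and the candidate covariates include depression, time since surgery, ostomy type, age, sex and stage. Only selection on characteristics that are not measured escapes adjustment.

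Fourth, the remedy is modest. Unintended steering can work through good guesses as well as through certainty, and best-guess accuracy barely moves. The share of assignments predictable with at least 75% probability, an arbitrary threshold, even rises from 33% to about 48% with sizes 4/6 and 59% with 2/4/6. This also stands and should be stated with the recommendation. Small fixed blocks do serve the stated aim of balance by sex within site, but varied blocks of similar size serve it nearly as well.

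**Conclusion.** The point holds as a limited weakness in allocation concealment. With a fixed, printed block size of 4 in each site-by-sex list, up to one third of assignments can be known in advance, about 80 of 240. The statement in 12.11 that selection bias will be avoided does not hold for those assignments.

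The one-third figure is exact for complete blocks. It assumes a person at the site who knows the block size and keeps an accurate tally by sex. It is a ceiling on what could be deduced, and nothing in the documents shows that steering has happened or will happen. Two premises are inferred: that envelopes are worked at the site, from the absence of contact with the data core at each randomization, and that the arms are open after assignment, from the nature of the intervention. The residual risk matters most for unmeasured characteristics such as motivation. The change is worth making because it costs little, not because a bias has been demonstrated.

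**What to change.** Generate each site-by-sex list with randomly varying block sizes, for example 4/6 or 4/6/8. Replace the block-size sentence in 7.2.2 with one that says sizes vary and are not disclosed to sites, and record the sizes in a document that sites do not see. Of the two examples, 4/6/8 leaves less certain knowledge and slightly lower guessing accuracy, at the price of a larger possible imbalance. Stratification by site and sex and local assignment can stay.

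In the same amendment, state who holds and who opens the envelopes, and reword 12.11 so that it describes the concealment actually achieved.

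The cost is regenerating six lists (or their unused parts, if recruitment has started) and a few sentences of text. The statistical price is a largest possible within-list imbalance of 3 (largest block 6) or 4 (largest block 8) instead of 2, which is small in lists averaging 40. Moving assignment to a central service while keeping fixed blocks of 4 would leave the one-third figure unchanged.
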